5.1.1.4 Neutralization of Endogenous IL-22 by Anti-Drug Antibodies

Though not seen in nonclinical and human studies to date, there is a possibility that efmarodocokin alfa may induce ADAs that neutralize endogenous IL-22 and thus be associated with an increased risk for opportunistic infections (including bacterial and fungal infections). ADAs may also reduce the therapeutic effect of efmarodocokin alfa. In addition, because IL-22 is involved in stimulating epithelial barrier repair, ADAs that neutralize endogenous IL-22 could impair epithelial barrier repair in the GI epithelium. These potential effects could be long-lasting if neutralizing ADAs are persistent.

Any patient who is found to test positive for ADAs to efmarodocokin alfa, including ADAs that may neutralize endogenous IL-22, should be followed, when possible, every 2 months for up to 6 months after the last dose of study drug, or until ADA titers are below the assay cut-point level, whichever occurs first.

Guidelines for management of patients who develop infections are provided in Section 5.1.2.3.

5.1.1.5 *Worsening of Clotting/Coagulation Dysfunction in High-Risk Populations due to Increased Fibrinogen*

Fibrinogen increases along with CRP are consistent with acute phase protein response, and are considered on-target effects of IL-22 signaling. A meta-analysis of clinical studies reported associations between plasma fibrinogen levels and the risks of coronary heart disease, stroke, other vascular mortality, and nonvascular mortality. However, whether the high fibrinogen levels are causal or are an effect of inflammation is not established (FSC 2005). In mice, infusion of fibrinogen was shown to induce a state of hyperfibrinogenemia, which was then associated with an increased risk of coagulation dysfunction and thrombosis (Machlus et al. 2011) but the translatability to humans remains uncertain (Ariens 2011; Klovaitė et al. 2011).

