Patients should be instructed to recognize the symptoms of a severe allergic (e.g., anaphylactic) or pseudoallergic (e.g., anaphylactoid) reaction and to contact a healthcare provider or seek immediate care in case of any such symptoms. Patients are to be provided with alert cards to remind them and a caregiver or partner of these instructions.

Guidelines for the management of patients who develop infusion-related reactions are provided in [Table 4](#).

Epithelial Tumors

Investigators should remain vigilant for signs or symptoms of cancer in scheduled study visits. Any signs or symptoms that could be suggestive of malignancy should be promptly and aggressively evaluated and reported to the Sponsor. If a patient develops epithelial tumors (as defined in [Table 4](#)) during the study, study drug must be discontinued permanently. In cases of newly diagnosed malignancy or epithelial high grade dysplasia, unstained slides and/or representative tissue blocks may be requested by the Sponsor for further evaluation and characterization.

Guidelines for the management of patients who develop epithelial tumors are provided in [Table 4](#).

Serious Infections

To assess for the potential development of an immune response, including neutralizing ADAs against endogenous IL-22, antibody samples will be obtained at baseline (Study Week 0), at regular intervals during treatment, and during the safety follow-up period and stored appropriately for further evaluation as needed.

Guidelines for the management of patients who develop infections are provided in [Table 4](#).

Hepatic Events

If treatment-emergent ALT or AST elevations are observed, ALT, AST, alkaline phosphatase, and total bilirubin tests (i.e. liver function tests [LFTs]) should be repeated within 48–72 hours to confirm the abnormality and to determine whether transaminases are increasing or decreasing.

For re-testing done locally or at a central laboratory facility, normal laboratory ranges should be recorded, results should be made available to trial investigators immediately, and the data should be included in the eCRF.

If treatment-emergent ALT or AST elevations are confirmed, other laboratory tests should be performed to rule out acute viral hepatitis (i.e., hepatitis A, B, C, D, or E),

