5.3.1 Adverse Event Reporting Period

Investigators will seek information on adverse events at each patient contact. All adverse events, whether reported by the patient or noted by study personnel, will be recorded in the patient's medical record and on the Adverse Event eCRF.

After informed consent for study entry has been obtained but prior to initiation of study drug, only serious adverse events caused by a protocol-mandated intervention (e.g., invasive procedures such as biopsies, discontinuation of medications) should be reported (see Section 5.4.2 for instructions for reporting serious adverse events).

After informed consent for study re-entry has been obtained (see Section 3.1.3) but prior to initiation of study drug, only serious adverse events caused by a protocol-mandated intervention (e.g., invasive procedures such as biopsies, discontinuation of medications) or prior study treatment should be reported (see Section 5.4.2 for instructions for reporting serious adverse events).

After initiation of study drug following study entry or study re-entry, all adverse events will be reported until 8 weeks after the final dose of study drug.

Any adverse event that occurs after completion of Week 52 and required safety follow-up assessments but prior to obtaining informed consent for study re-entry should be captured on the General Medical History and Baseline Conditions eCRF rather than the Adverse Event eCRF, unless it is a serious adverse event related to prior study treatment.

Instructions for reporting adverse events that occur after the adverse event reporting period are provided in Section 5.6.

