Appendix 1 Schedule of Activities (cont.)

- ^w ADA samples may be used to assess PK if needed. ADA samples should be collected in patients with signs and symptoms of serious opportunistic infections or infusion-related reactions, if not already scheduled to be collected at that timepoint. For patients receiving efmarodocokin alfa Q4W, ADA samples should be collected at treatment initiation (prior to dosing) and every 12 weeks thereafter.
- ^x Stool samples should be obtained prior to bowel preparation.
- ^y Patients with UC are to record stool frequency and rectal bleeding in the daily diary throughout the study (see Section 4.5.5.4). Patients with CD are to record loose-stool frequency, abdominal pain severity, and general well-being in the daily diary throughout the study (see Section 4.5.5.4).
- ^z Patients who do not meet criteria for clinical remission will receive efmarodocokin alfa 60 µg/kg IV Q4W until clinical remission is achieved.
- ^{aa} Video recordings should be taken of the entire endoscopic procedure, starting from insertion into the bowel. Biopsies should be performed upon withdrawal of the endoscope from the bowel. Technical instructions for video recording and biopsy collection are provided in the laboratory manual.
- ^{bb} Patients will undergo annual colonoscopies for colon cancer surveillance. The colonoscopies should include removal of any adenomatous polyps and performance of multiple random mucosal tissue samples (see Section 4.5.5.6). This colonoscopy can substitute for the flexible sigmoidoscopy (for patients with UC) or be part of the ileocolonoscopy (for patients with CD) if the procedures are scheduled to occur during the same time period.
- ^{cc} MCS is a composite of four assessments, each having a scoring range of 0–3: stool frequency, rectal bleeding, endoscopy, and PGA.
- ^{dd} pMCS is a composite of three assessments from the MCS, each having a scoring range of 0–3: stool frequency, rectal bleeding, and PGA.
- ^{ee} pMCS may be performed at an unscheduled visit as determined by the investigator or Sponsor.

Appendix 2

Mayo Clinic Score

Please respond to the following questions after reviewing the patient's Signs and Symptoms of Ulcerative Colitis Daily Diary at each visit as per the schedule of activities.

1. Stool frequency

- 0=Normal
- 1=1–2 stools/day more than normal
- 2=3–4 stools/day more than normal
- 3=>4 stools/day more than normal

2. Rectal bleeding

- 0=None

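### ADA-positive patients who are permanently off drug or out of the study may be contacted for up to 6 months, but most new infections found at the month 4 and 6 contacts have no required recording route

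*Combined protocol and SAP*

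**What the plan says.** **The follow-up.** Section 5.1.1.4 considers that ADAs might neutralize the patient's own IL-22 and so "be associated with an increased risk for opportunistic infections (including bacterial and fungal infections"). It also mentions a weaker drug effect and poorer epithelial barrier repair, and adds: "These potential effects could be long-lasting if neutralizing ADAs are persistent". Any patient who tests positive "should be followed, when possible, every 2 months for up to 6 months after the last dose of study drug". The contacts can stop sooner if the antibodies clear, since the same sentence gives a second end point: "or until ADA titers are below the assay cut-point level, whichever occurs first". The section then points to the infection guidance in 5.1.2.3.

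**The link to infection elsewhere.** Under its serious-infections heading, 5.1.2.3 says that "antibody samples will be obtained at baseline (Study Week 0), at regular intervals during treatment, and during the safety follow-up period". Appendix 1 footnote w says that "ADA samples should be collected in patients with signs and symptoms of serious opportunistic infections or infusion-related reactions", if none is already scheduled.

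**The reporting period.** Section 5.3.1 opens with "Investigators will seek information on adverse events at each patient contact", but then limits the period: "all adverse events will be reported until 8 weeks after the final dose of study drug". Section 5.4.2.2 sets the same limit for serious adverse events and adverse events of special interest, and footnote l repeats it for the adverse-event row of the schedule. After that, 5.6 and footnote l ask only for serious events believed related to earlier study drug. None of these sections makes an exception for ADA-positive patients.

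**The concern.** The plan names a possible late harm, asks for contacts that run well past 8 weeks, and closes the adverse-event record before most of that time has passed. At month 4 or 6 a site could draw a titer, learn of a new infection, and have no duty to record it unless it is serious and believed related.

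The study's main objective is long-term safety, and Section 1.3 gives the immunogenicity of intermittent treat-to-remission dosing as a reason for running it. A late titer without a matching infection record is less useful for that purpose than it could be, at contacts the plan already requests.

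**Working it through.** The plan gives no figure on this point to reproduce. The check sets the two time windows side by side and then asks which events still have a route.

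**Inputs**
- Reporting closes at 8 weeks = 8 × 7 = 56 days after the final dose (5.3.1, 5.4.2.2, 5.6, footnote l).
- ADA contacts fall at months k = 2, 4 and 6 after the last dose (5.1.1.4).
- The safety follow-up visit is at 8 weeks ± 5 days (3.1.6, Appendix 1).
- Month length is not defined. Assumed range: 28 days, or 365.25/12 = 30.44 days.

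**Timing.** Weeks past the close = (k × month length − 56) / 7.

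| Contact | 28-day month | Past close | Calendar month | Past close |
|---|---|---|---|---|
| Month 2 | 56 d = 8.0 wk | 0.0 wk | 60.9 d = 8.7 wk | 0.7 wk |
| Month 4 | 112 d = 16.0 wk | 8.0 wk | 121.8 d = 17.4 wk | 9.4 wk |
| Month 6 | 168 d = 24.0 wk | 16.0 wk | 182.6 d = 26.1 wk | 18.1 wk |

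The safety follow-up window runs from (56 − 5)/7 = 7.3 to (56 + 5)/7 = 8.7 weeks, so the month 2 contact can be the same visit. The month 4 and 6 contacts cannot. At most 16.0 of 24.0 weeks (67%) or 18.1 of 26.1 weeks (69%) of the follow-up lies past the close.

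**Routes at month 4 or 6 for a patient permanently off drug or out of the study**
- Serious infection believed related: captured by 5.6, with no end date.
- Infection that began before week 8 and is unresolved: followed under 5.5.1.
- New serious infection judged unrelated: no required route. This includes a fatal one, because 5.3.5.9 sends later deaths to 5.6. COVID-19, an event of special interest under 5.2.3, also loses its separate duty at 8 weeks under 5.4.2.2.
- New non-serious infection: no required route.

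**Patients still in off-drug observation.** The adverse-event row is marked at their visits, but footnote l governs that row. Other text carries no 8-week limit: footnote o and 4.5.3 send new clinically significant examination findings to the Adverse Event eCRF, 4.5.2 asks for an interval history at each follow-up examination, and 4.4 has concomitant medication recorded to the final visit. Whether the last dose was the final one is also known only later.

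These patients already have visits in the relevant time. Remission visits fall 4, 8 and 16 weeks after remission and every 8 weeks from then (Appendix 1, footnote e). Assume remission is found d = 0 to 4 weeks after the last dose. Visits after week 8 and up to week 26.1 from the last dose are then: d = 0, weeks 16 and 24; d = 1, weeks 9, 17 and 25; d = 2, weeks 10, 18 and 26; d = 3, weeks 11 and 19; d = 4, weeks 12 and 20. That is 2 to 3 visits.

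**The case against.** The strongest reply is that two windows of different length are not a contradiction. The 5.1.1.4 follow-up stops on titer and is made only when possible, so it can be read as titer follow-up. The section states no single purpose, and nothing says these contacts were meant to collect every infection. This stands: the point is a gap in capture, not a contradiction.

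Second, the infections of most interest have a route. Section 5.6 has no end date, Table 6 treats an event as related unless evidence points elsewhere, and 5.2.2 counts a significant medical event as serious. This narrows the gap but does not close it. Patients who have permanently stopped drug may be on rescue therapy (3.1.6), which under 4.4.1 includes corticosteroids, immunosuppressants and TNF inhibitors. These give a ready alternative cause, so some serious infections could be judged unrelated.

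Third, 5.3.1 has investigators ask about adverse events at each contact. The same section sets the 8-week limit, so at best the text conflicts with itself for late contacts.

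A reader might go further and infer that observation patients have no route either. The documents do not support that, given footnote o, 4.5.2, 4.5.3 and 4.4. Nor can 67% to 69% be read as a share of infections lost: it is a maximum of calendar time, and the documents give no infection rate and no split by seriousness or causality.

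**Conclusion.** The gap is real but minor. It is clear for ADA-positive patients who have permanently stopped drug or left the study; for those in off-drug observation the wording is ambiguous. The events without a required route are new non-serious infections and serious infections judged unrelated, found 8.0 to 9.4 weeks (month 4) or 16.0 to 18.1 weeks (month 6) after the close. Follow-up may be shorter if titers clear or contact is not possible.

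Few patients are likely to be affected. Section 1.2.2 reports ADAs in 1 of 44 subjects in the single-dose Phase Ia study, after a low subcutaneous dose, and no treatment-emergent ADAs in the multiple-dose Phase Ib study, where two participants were positive at baseline. Section 5.1.1.4 covers any positive patient, and incidence under up to 2 years of 60 µg/kg Q4W is unknown, so no count is projected.

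A reader might also infer that the Section 6.7 description of safety by ADA status is biased. It is not biased by this gap, because the 8-week limit applies to ADA-positive and ADA-negative patients alike. No efficacy endpoint or analysis population changes.

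**What to change.** Add to 5.3.1: *For ADA-positive patients followed under Section 5.1.1.4, infections of any seriousness identified at those contacts are recorded on the Adverse Event eCRF regardless of causality.* Put matching text in 5.4.2.2, 5.6 and Appendix 1 footnote l. Section 5.6 must be included because it defines the period as ending at 8 weeks and would otherwise conflict with the new sentence. Section 5.3.1 already has special rules for re-entry patients, so the addition fits its structure.

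Keep the follow-up conditional on being possible, and add no visits. List these late infections separately, with ADA titer and rescue therapy. Do not compare them with ADA-negative patients, because late events would then be sought in one group only.

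The cost is one sentence in four places, a little extra data entry for few patients, and possibly one line in the consent form if it states the recording period (the consent pages are not among the documents). With no visit added, the end-of-study date in 3.2 does not move.

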5.1.2 Management of Patients Who Experience Adverse Events

At this stage of development, the efmarodocokin alfa safety profile is not completely characterized. For any treatment-emergent adverse event that the investigator believes may be related to efmarodocokin alfa, the investigator should consider whether the benefit-risk favors continued dosing for that individual patient (i.e., if the adverse event is improving and if a clear alternate cause can be identified).

Guidelines for the monitoring and management of patients who experience specific adverse events are provided in Table 4.

5.1.2.1 Dose Modifications

The dose of efmarodocokin alfa should not be modified when managing individual patients who experience adverse events.

5.1.2.2 Treatment Interruption

Study treatment may be temporarily suspended in patients who experience a treatment-emergent adverse event considered to be related to study drug. If the event resolves to Grade 2 or better, treatment will resume at the next scheduled dose. If more than one scheduled dose will be missed because of an on-going adverse event, the patient should be permanently discontinued from treatment, unless resumption of treatment is *determined* following investigator discussion with the Medical Monitor. Study treatment may be suspended for reasons other than a treatment-emergent adverse event (e.g., surgical procedures) *after discussion with the* Medical Monitor. The investigator and the Medical Monitor will determine the acceptable length of treatment interruption.

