ADA=anti-drug antibody; AESI=adverse event of special interest; LFT=liver function test; PK=pharmacokinetic; ULN=upper limit of normal.

Table 4 Guidelines for Management of Patients Who Experience Specific Adverse Events (cont.)

Event	Action to Be Taken
Infection	
Grade 1 or 2	
 Continue study drug.
Grade 3	
 Withhold study drug. Collect PK and ADA sample if not collected at study visit, and treat according to local standards. If the infection is clearly not study-drug related (i.e., there is a clear alternative explanation for the infection), the infection and symptoms are fully resolved at least 1 week prior to the next scheduled dose, and any treatment for the infection has been completed at least 1 week prior to the next scheduled dose, consult the Medical Monitor to determine if study drug can be resumed. If these conditions are not met or the Medical Monitor indicates that study drug should not be resumed, permanently discontinue study drug.
Grade 4	
 Permanently discontinue study drug. Collect PK and ADA sample if not collected at study visit, and treat according to local standards.
Suspected or confirmed COVID-19 infection	
Grades 1–3	
 Withhold study drug If the infection and symptoms are fully resolved at least 1 week prior to the next scheduled dose, and any treatment for the infection has been completed at least 1 week prior to the next scheduled dose, consult the Medical Monitor to determine if study drug can be resumed. If these conditions are not met or the Medical Monitor indicates that study drug should not be resumed, permanently discontinue study drug.
Grade 4	
 Permanently discontinue study drug.
Epithelial tumor	
New malignancy, unresectable colonic mucosal dysplasia, or any high-grade colonic mucosal dysplasia	
 Permanently discontinue study drug.
New cervical intraepithelial neoplasia of Grade >1, cervical smear indicating the presence of adenocarcinoma in situ, or high-grade squamous intraepithelial lesion	
 Permanently discontinue study drug.

ADA=anti-drug antibody; AESI=adverse event of special interest; LFT=liver function test; PK=pharmacokinetic; ULN=upper limit of normal.

Table 4 Guidelines for Management of Patients Who Experience Specific Adverse Events (cont.)

Event	Action to Be Taken

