Grade 1	
 Continue study drug and monitor closely for worsening of symptoms.
Grade 2 or 3	
 Treat as per local standard of care. Withhold study drug until the event resolves to a Grade 1 or lower. Report event to Sponsor in an expedited manner as an AESI (see Section 5.2.3).
Grade 4	
 Permanently discontinue study drug. Notify Medical Monitor and offer medical management per local standard of care, and follow for safety. Report event to Sponsor in an expedited manner as an AESI (see Section 5.2.3).
Efmarodocokin alfa-related adverse events not described above	
Grade 1 or 2	
 Continue study drug.
Grade 3	
 Withhold study drug. If event resolves to Grade 2 or better, resume study drug at the next scheduled dose. If more than one scheduled dose will be missed because of an on-going adverse event, permanently discontinue study drug.
Grade 4	
 Permanently discontinue study drug, offer medical management per local standard of care, and follow for safety.

ADA=anti-drug antibody; AESI=adverse event of special interest; LFT=liver function test; PK=pharmacokinetic; ULN=upper limit of normal.

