5.2.3 Adverse Events of Special Interest (Immediately Reportable to the Sponsor)

Adverse events of special interest are required to be reported by the investigator to the Sponsor immediately (i.e., no more than 24 hours after learning of the event; see Section 5.4.2 for reporting instructions). Adverse events of special interest for this study are as follows:

- Cases of potential drug-induced liver injury that include an elevated ALT or AST in combination with either an elevated bilirubin or clinical jaundice, as defined by Hy's Law (see Section 5.3.5.7)
- Suspected transmission of an infectious agent by the study drug, as defined below
 - Any organism, virus, or infectious particle (e.g., prion protein transmitting transmissible spongiform encephalopathy), pathogenic or non-pathogenic, is considered an infectious agent. A transmission of an infectious agent may be suspected from clinical symptoms or laboratory findings that indicate an infection in a patient exposed to a medicinal product. This term applies only when a contamination of the study drug is suspected.
- Any adverse event leading to discontinuation of study drug
- New or worsening neurologic signs and symptoms that are consistent with a diagnosis of progressive multifocal leukoencephalopathy
- Suspected or confirmed COVID-19 infection
- *Grade ≥2 thromboembolism or deep vein thrombosis*

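### Section 5.1.2.2 and Table 4 differ on restarting treatment after some drug-related adverse events, and no general order of precedence is stated

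*Combined protocol and SAP*

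**What the plan says.** Section 5.1.2.2 covers every drug-related treatment-emergent event and excludes no event type: "Study treatment may be temporarily suspended in patients who experience a treatment-emergent adverse event considered to be related to study drug". It continues: "If the event resolves to Grade 2 or better, treatment will resume at the next scheduled dose". If more than one scheduled dose would be missed, "the patient should be permanently discontinued from treatment, unless resumption of treatment is" decided on "following investigator discussion with the Medical Monitor".

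Table 4, in Section 5.1.2.3, sets actions by event and grade:

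- **Dermatologic, Grade 3**, and the **catch-all row** (drug-related events without a row of their own), Grade 3: withhold, and resume once the event is Grade 2 or better (with topical treatment, in the dermatologic row). Then: "If more than one scheduled dose will be missed because of an on-going adverse event, permanently discontinue study drug". Neither row has an exception.
- **Infection, Grade 3**: withhold. Restart goes to the Medical Monitor only under conditions, the first of which begins "If the infection is clearly not study-drug related (i.e., there is a clear alternative explanation for the infection". The infection must also be fully resolved, and its treatment finished, at least 1 week before the next dose. Otherwise the drug is stopped permanently.
- **Thromboembolism or deep vein thrombosis, Grade 2 or 3**: "Withhold study drug until the event resolves to a Grade 1 or lower". Section 5.1.1.5 gives the same threshold.

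The introduction to Section 5.1.2 refers to Table 4 for specific events but does not say that it overrides Section 5.1.2.2. Section 5.2.3 includes "Any adverse event leading to discontinuation of study drug" among the adverse events of special interest, reportable within 24 hours.

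**The concern.** This is a safety and tolerability study, and the two passages decide whether a patient is re-exposed after a drug-related event. They also bear on what is counted. A discontinuation for an adverse event is an adverse event of special interest. Section 6.4 summarises safety by total dose, number of infusions, number of consecutive monthly doses and maximum cumulative dose in consecutive months. If two sites could each follow the protocol and act differently on the same event, part of the variation in those summaries would come from the wording and not from the drug. A patient could also be dosed under one passage when the other forbids it.

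**Working it through.** The plan gives no figure to reproduce. The check is a row-by-row comparison of Table 4 with Section 5.1.2.2, limited to drug-related events, because that is the scope of Section 5.1.2.2.

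| Related event | Section 5.1.2.2 | Table 4 | Result |
|---|---|---|---|
| Dermatologic, Grade 3: restart grade | Grade 2 or better | Grade 2 or better | Same |
| Dermatologic, Grade 3: more than one missed dose | Permanent stop, unless resumption is settled with the Medical Monitor | Permanent stop | Same default; exception missing from Table 4 |
| Catch-all, Grade 3: restart grade | Grade 2 or better | Grade 2 or better | Same |
| Catch-all, Grade 3: more than one missed dose | Permanent stop, unless resumption is settled with the Medical Monitor | Permanent stop | Same default; exception missing from Table 4 |
| Infection, Grade 3, improving to Grade 2 | Resume at next scheduled dose | Permanent stop, because the not-drug-related condition fails | Different |
| Thromboembolism or deep vein thrombosis, Grade 3 improving to Grade 2 | Resume at next scheduled dose | Keep withholding until Grade 1 or lower | Different |

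**Does the more specific text settle it?** Not for the catch-all row. That row is itself a general rule for drug-related events, so it covers the same class as Section 5.1.2.2. The missing exception is also hard to read as shorthand. Table 4 names the Medical Monitor in its infusion-reaction, infection, COVID-19, hepatic and Grade 4 thrombosis rows, so silence in the dermatologic and catch-all rows reads as intended.

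**When does the missing exception matter?** Dosing is every 4 weeks. Let t be the weeks from the last dose to onset, with 0 ≤ t < 4.

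- The first withheld dose falls due 4 − t weeks after onset, which is up to 4 weeks.
- The second falls due 8 − t weeks after onset, which is more than 4 and up to 8 weeks.

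The texts part when a related Grade 3 event has not improved to Grade 2 by the second date, or earlier if that is foreseen, since both refer to doses that will be missed.

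**Is precedence stated elsewhere?** Only in part. Section 4.6.1 sends other serious or severe infections to Section 5.1.2.3 and Table 4. Section 5.1.1.5 repeats the Grade 1 threshold for thrombosis and points to Section 5.1.2.3, where the thrombosis paragraph points to Table 4. None of these addresses the dermatologic or catch-all rows. Section 4.3.2 sends sites to Section 5.1.2 as a whole, which contains both texts.

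**The case against.** The best defence is that Table 4 is the working instruction and Section 5.1.2.2 only background. For severe infection and for thrombosis this has force: the cross-references above lead to Table 4 each time, so a careful site would probably act on it. What remains is that Section 5.1.2.2 says treatment will resume and does not exempt these events. For the dermatologic and catch-all rows the defence fails, because no cross-reference resolves them.

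A second defence is that resumption after more than one missed dose runs through the Medical Monitor, a sponsor-side check that limits divergence between sites. That is fair as a limit on the risk. It does not make the texts agree: a site using that route departs from Table 4, and Section 9.2 does not allow prospective requests to deviate.

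A third is that the safety analysis is descriptive, with no hypothesis test. This also stands. No error rate is at stake, and no size for any distortion can be derived.

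Several stronger readings are tempting, but the documents do not support them:

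- **That the missed-dose rules are opposite.** Both default to permanent discontinuation; only the exception differs.
- **That restart grades conflict throughout.** They are identical in the dermatologic and catch-all rows.
- **That a thrombosis starting at Grade 2 would be dosed under Section 5.1.2.2.** Such an event has not resolved to Grade 2, and nothing in that section orders dosing.
- **That the missing missed-dose limit in the thrombosis row is a contradiction.** It is a silence that the general rule can fill.
- **That the Grade 4 permanent stops contradict Section 5.1.2.2.** That section permits temporary suspension and does not require it; an event that ends treatment outright is not a suspension. The Grade 3 infection row differs because it begins by withholding.

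**Conclusion.** The inconsistency is real and confined to four event classes. In two (related Grade 3 dermatologic events and the catch-all row) the only difference is the Medical Monitor exception, and nothing in the documents resolves it. In the other two (related Grade 3 infection, and related thrombosis improving from Grade 3 to Grade 2) the literal instructions differ, although cross-references favour Table 4.

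The number of patients affected cannot be estimated, because the documents give no rate for related Grade 3 events lasting into a second dosing date. Section 5.1.1.1 describes mostly mild, sometimes moderate skin reactions in healthy volunteers resolving within about 2 weeks. If that carried over to Grade 3 events in patients, which is an assumption, few dermatologic events would reach the 4-to-8-week point.

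A reader might infer that identical patients are in fact being restarted at one site and stopped at another. The documents do not show this. Divergence in re-exposure, discontinuations and cumulative exposure is a foreseeable risk. It merits correction because those quantities are central to a safety study and the correction is cheap. The conclusion rests on reading Section 5.1.2.2 as applying to all drug-related events, as its wording states.

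**What to change.** Reconcile Section 5.1.2.2 and Table 4 so that, for each event class, both give the same answer on three items: the condition for restart, the consequence of missing more than one dose, and whether a Medical Monitor provision applies. Then add one sentence stating which text governs if they still differ.

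The precedence sentence should not be used to settle the clinical question by default. Making Table 4 prevail would remove the Medical Monitor exception from the dermatologic and catch-all rows; making Section 5.1.2.2 prevail would displace the infection and thrombosis criteria. The clinical team should first decide which rule applies to each class and whether event-specific criteria stay, and the wording should follow. No clinical rule is proposed here.

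The cost is wording at the next amendment and a memo to sites, with no added patients or procedures. Depending on the choice, some discretion may be lost for a few events.
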